8.5.4 Pharmacokinetic Analyses

Through will be summarized by dose and study day.

The image consists of several horizontal bands of varying shades of gray. A large, solid black band occupies the top half of the frame. Below this is a thick, solid black band. A single, thin white horizontal bar is positioned in the middle of the image. Below the white bar is a thick, solid black band. At the bottom of the image, there is a series of alternating black and white rectangular blocks, resembling a barcode or a series of steps. The entire image is rendered in a high-contrast, black-and-white style, with significant noise and pixelation, giving it a grainy, low-resolution appearance.

8.5.7 *Outcomes Research Analyses*

Not applicable.

8.5.8 *Other Analyses*

8.5.8.1 Immunogenicity Analysis

Proportion of subjects with BMS-931699 induced antibody response and titers over time will be summarized.

8.6 Interim Analyses

8.6.1 *Interim Safety/RO Real Time Analysis at Day 29*

When at least 6 patients per treatment arm have either reached Study Day 29 or discontinued, an interim analysis (IA) for safety and RO will be performed. The safety analysis will focus on incidence and severity of all adverse events (AEs), serious AEs and pre-established Events of Special Interest such as infection AEs and any other safety analysis requested by DMC. For RO: the median RO at Day 29 for each treatment arm will be calculated. Based on the results of this interim analysis, a decision will be taken regarding the doses that will be carried forward into Part 2 of the study. Specifically, dosing regimens originally included in Part 1 may be discontinued and/or new dosing regimens may be added according to the following criteria:

Safety:

The DMC in conjunction with an unblinded internal monitoring team may require one or more doses to be discontinued if stopping criteria are met or other safety signals arise that the Medical Monitor and/or DMC consider of sufficient concern.

Receptor Occupancy:

- If median RO of any dose is < 20%, the sponsor may consider dropping that dose
- If the median RO for all doses is > 90% the sponsor may consider adding or replacing a dose in Part 2 of the study to ensure an adequate pharmacodynamic range (dose not to exceed 12.5 mg weekly)

Dose decrease and/or reduction of frequency of administration may also be considered if RO results fall outside the parameters indicated above. This adjustment may occur for safety reasons or in case unforeseen RO profiles observed in SLE patients. The decision to adjust dose and/or frequency will be taken after review of the data by the clinical team.

8.6.2 *Interim Analysis for Futility and Dose Adaption at Day 85*

After 30 subjects per treatment arm (including the subjects from Part 1) have completed at least 84 days of the treatment period or discontinued the treatment, an interim analysis will be conducted to assess the futility of the BMS-931699 dose arms and the overall safety. The results of the interim analysis will be reviewed by an unblinded sponsor team who will provide recommendations to the blinded study team. The blinded study team will make the decision. The unblinded BMS team may recommend to:

- maintain the current design;
- drop a certain dose arm(s) and equally randomize the remaining unallocated subjects to the remaining arms;
- stop the study if all dose arms need to be dropped for safety or futility reasons.

The interim analysis for futility and dose adaption will be performed on the BICLA response at Day 85 of those 30 subjects per arm and BICLA response at Day 169 of those subjects who have completed 168 days of treatment or discontinued the treatment using a Bayesian predictive approach.²² This analysis assumes that the BICLA at Day 85 and at Day 169 in the subjects who have not yet been observed will be similar to what were observed for the subjects included at the interim analysis at Day 85 and Day 169, respectively. As such the unobserved data will be simulated from the predictive distribution conditional on the interim data and the prior distribution of the treatment difference (using a non-informative prior). Under the Bayesian framework, the posterior distribution of the treatment difference (BMS-931699 active dose – Placebo) will be constructed to determine the predictive probability of a successful outcome (ie, reach statistical significance) at the planned end of the trial for each dose arm. Based on computer simulations of the operating characteristics of the study design, the futility threshold in this interim analysis is set to 0.2. For the comparison of interest, if the predictive probability of a

successful outcome at the planned end of the trial falls below 0.2, that BMS-931699 dose arm is deemed futile in terms of BICLA response. However, the final futility will also incorporate the results from SRI(4), ACR28 and some biomarkers (C3, C4, ANA and anti-dsDNA).

The proposed stopping rules at the interim analysis, based on the futility assessment and the overall safety assessment, are as follows:

- Rule 1: Drop the futile dose arm(s) and the dose arm cannot be dropped until the lower dose arm has been dropped.
- Rule 2: Drop the dose arm(s) with safety issues identified;
- Rule 3: If safety issues are identified in all dose arms or all dose arms are futile, stop the study.

In case dosing arms are dropped following the interim analysis, the remaining unallocated subjects will be randomized into the remaining arms.

If the predictive probability of success for each active arm versus placebo is greater than or equal to 0.9, then the BMS team may also recommend adding an additional dose arm at lower dose level than current active doses to explore the suboptimal dose.

In that case, the remaining un-allocated subjects with up to 40 additional subjects will be randomized into the remaining arms and the new dose arm based on the new randomizations schedule.

8.7.1 Analysis for the Long-Term Extension Period

The LTE period starts when a subject receives at least one post Day 169 dose. The analysis based on this period is descriptive in nature.

8.7.1.1 Populations of Analysis

All Subjects who received at least one dose post Day 169.

8.7.1.2 Demographics and Baseline Characteristics

Categorical parameters will be summarized using frequency counts and percentages. Continuous parameters will be summarized through means, SD, median, and range. The baseline (Day 1) is defined as the start of study medication (the same as the baseline in the short-term period). The baseline results will be based on LTE analysis population.

8.7.1.3 Efficacy Analyses

For continuous secondary endpoints (eg, SLEDAI, MDGA etc.) point estimates and 90% confidence intervals for mean change from baseline to subsequent time points (in LTE period) within each treatment groups will be provided. For binary endpoints (BICLA Response, SRI(X) etc.), point estimates and 90% confidence intervals (CIs) will be provided using normal

approximation within each treatment group. The assessment windows for LTE period will be based on the first LTE dose date; the baseline to assess responses or changes still refers to the Day 1 assessment (the same as the baseline in the short-term period). The results will be presented by treatment groups. All analyses will be based on as-observed data; hence no imputation will be implemented. No statistical testing including p-value computation will be performed.

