1.3.4 Long-Term Extension Period Objectives

Assess the long term clinical safety, tolerability and efficacy of lulizumab pegol.

similar to the reported plasma volume, indicating very limited extravascular distribution. The [REDACTED]

[REDACTED]

[REDACTED]

[REDACTED]

[REDACTED]

[REDACTED]

[figure not shown]
[figure not shown]
[REDACTED] 16

[REDACTED]

[REDACTED]

[REDACTED]

The MAD study IM128003 was performed in 24 subjects (3 cohorts of 8 subjects) treated for

Intense safety monitoring will be put in place during the entire study (short-term and long-term extension periods), allowing early detection of any safety signals. Specifically, the following measures will be put in place:

- Patients will undergo safety evaluation at each clinic visit.
- Investigator will conduct safety evaluation before dosing.
- Continuous internal data review by unblinded clinical monitoring team.
- Monitoring team to refer to independent external DMC any safety issue deemed to be of relevance.
- Independent external DMC to meet at regular intervals throughout the entire study to review all data (frequency to be determined in conjunction with DMC).
- Stopping rules to be implemented under DMC guidance.

DMC and internal safety monitoring activities initiated in Part 1 will continue into Part 2 and will be ongoing until the end of the study, including the long-term extension.

In summary, the potential overall benefit ratio for BMS-931699 treated subjects in this trial appears favorable. In order to minimize the overall risk to participating subjects, this protocol has inclusion and exclusion criteria appropriate to the population and proposed treatments, exclusionary screening tests [chest x-ray, Quantiferon Gold testing (or other interferon gamma release assay test, such as T-SPOT) wherever appropriate, risk factor/age specific breast screening, medical history], and specific follow-up safety assessments. In addition, the AEs and SAEs will be reviewed on an ongoing basis by the medical monitors and pharmacovigilance group to look for trends and any safety issues.

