3.3.3 Women of Childbearing Potential

Women of childbearing potential (WOCBP) is defined as any female who has experienced menarche and who has not undergone surgical sterilization (hysterectomy or bilateral oophorectomy) and is not postmenopausal. Menopause is defined as 12 months of amenorrhea in a woman over age 45 in the absence of other biological or physiological causes. In addition, females under the age of 55 years must have a documented serum follicle stimulating hormone, (FSH) level $> 40 \text{ mIU/mL}$ to confirm menopause.

Females treated with hormone replacement therapy, (HRT) are likely to have artificially suppressed FSH levels and may require a washout period in order to obtain a physiologic FSH level. The duration of the washout period is a function of the type of HRT used. The duration of the washout period below are suggested guidelines and the investigators should use their judgment in checking serum FSH levels. If the serum FSH level is $> 40 \text{ mIU/ml}$ at any time during the washout period, the woman can be considered postmenopausal.

- 1 week minimum for vaginal hormonal products (rings, creams, gels)
- 4 week minimum for transdermal products
- 8 week minimum for oral products

Other parenteral products may require washout periods as long as 6 months.

3.3.4 *Criteria for Long-Term Extension*

Subjects who enter the short-term period according to the eligibility criteria outlined in Sections 3.3.1 and 3.3.2, and who complete 24 weeks on study medication are eligible for participation in the LTE period. The LTE period will remain blinded but will no longer be placebo controlled, as subjects completing Day 169 in the placebo arm will be re-randomized to existing active arms.

A separate informed consent must be signed to enter the LTE period.

The class and dose of background therapies is recommended to remain the same as in the short term period. However, temporary rescue therapy with prednisone (or prednisone equivalent) to transiently manage SLE disease activity may be instituted. The increase in prednisone should not exceed a total daily dose of 20 mg, and must return to the previous stable dose within 14 days. Subjects requiring more than 14 days of rescue therapy will be discontinued.

The use of cyclophosphamide, any intravenous, any intra-articular or biologic agent remains prohibited during LTE. Any changes to or new concomitant therapies must be recorded on the CRF.

[REDACTED]

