The use of rescue therapies other than prednisone (or prednisone equivalent), such as cyclophosphamide, any intravenous, any intra-articular or biologic agent is prohibited.

Any changes to or new concomitant therapies must be recorded on the CRF.

4.5.4.2 *Long-Term Extension Period*

The class and dose of background therapies is recommended to remain the same as in the short term period. However, temporary rescue therapy with prednisone (or prednisone equivalent) to transiently manage SLE disease activity may be instituted. The increase in prednisone should not

exceed a total daily dose of 20 mg, and must return to the previous stable dose within 14 days. Subjects requiring more than 20 mg/day for more than 14 days of rescue therapy will be discontinued from the LTE.

The use of rescue therapies other than prednisone (or prednisone equivalent), such as cyclophosphamide, any intravenous, any intra-articular or biologic agent remains prohibited during LTE.

Any changes to or new concomitant therapies must be recorded on the CRF.

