5.4.1.2 Long-Term Extension Period

Primary efficacy assessments during the long-term extension will be the same as in the short-term period, in order to assess long-term durability of response.

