8.3.2.3 Pharmacokinetic Endpoints

Ctrough: Trough level serum concentration of BMS-931699 at time points specified in Section [5.5](#).

8.3.2.5 *Immunogenicity*

Proportion of subjects with BMS-931699 induced antibody response at visit specified in [Table 5.5.3](#).

8.4 *Endpoints for Long-term Extension Period*

During the LTE period, the following endpoints will be assessed cumulatively (safety) and over time (efficacy).

8.4.1 *Safety Endpoints*

- Incidence and severity of all Adverse Events (AEs), Serious AEs, and pre-established Events of Special Interest
- Incidence and severity of clinically significant abnormalities in general laboratory tests

8.4.2 *Efficacy Endpoints*

- Proportion of subjects who achieve BICLA response (BICLA response rate)
- Proportion of subjects who meet response criteria for the SLE Responder Index (SRI) [SRI(4), SRI(5) and SRI(6)]

- CLASI score
- ACR 28 joint count of tender and swollen joints
- Overall BILAG-2004 score
- Overall SLEDAI-2K score
- Overall MDGA score
- The cumulative corticosteroid and immunosuppressant use
- Proportion of patients reaching a Major Clinical Response and Partial Clinical Response
- Fatigue, based on the FACIT
- Quality of life, based on SF-36

8.4.3 *Pharmacokinetic Endpoints*

Ctrough: Trough level serum concentration of BMS-931699 at time points specified in Section 5.5.

8.4.5 *Immunogenicity*

Proportion of subjects with BMS-931699 induced antibody response at visits defined in Table 5.1-3

8.5 *Analyses for the Short-Term Period*

8.5.1 *Demographics and Baseline Characteristics*

Frequency distributions of gender and race will be tabulated. Summary statistics for age, body weight, height, and Body Mass Index (BMI) will be tabulated.

8.5.2 *Efficacy Analyses*

Primary efficacy analysis:

The Chi-square tests will be used to compare the BICLA response rates at Day 169 between each of the active treatment arms and the placebo arm. The Chi-square p-value will be provided for each comparison between the active treatment and the placebo arm. In addition, the difference of the response rates between each active treatment and the placebo will be estimated and their corresponding 90% confidence interval will be calculated. No adjustment will be made for multiplicity.

Secondary efficacy analysis:

- Proportion of subjects who meet response criteria for the SLE Responder Index(4) [SRI(4)], SRI(5) and SRI(6) at Day 169

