### ***8.1.3 Evaluation of Major Clinical Response and Partial Clinical Response***

Major and Partial Clinical responses are defined as:

- **Major Clinical Response:** a patient with BILAG C scores or better at 6 months with no new BILAG A or BILAG B scores AND maintenance of response with no new BILAG A or B scores between 6 and 12 months.
- **Partial Clinical Response:** a patient with BILAG C scores or better at 6 months with no new BILAG A or BILAG B scores and maintenance of response without a flare for 4 months.

If a subject is not meeting any of the above criteria, the response status will be set to non-responder.

If a subject has any missing data at a particular visit, the subject will be excluded from the analysis at that particular visit. The details will be provided in the LTE SAP.

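### The as-observed analysis of the long-term extension drops known failures from later visits, so its response rates are conditional on staying in and never fall below the all-entrants rate

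*Protocol*

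**What the plan says.** **Purpose.** The LTE objective in protocol 1.3.4 is: "Assess the long term clinical safety, tolerability and efficacy of lulizumab pegol". Sections 5.4.1.2 and 5.4.2.2 carry the short-term efficacy assessments into the LTE "in order to assess long-term durability of response". Section 8.4.2 lists BICLA, SRI(4), SRI(5), SRI(6) and Major and Partial Clinical Response among the LTE efficacy endpoints.

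**Population and missing data.** Section 8.7.1.1 defines the LTE population as "All Subjects who received at least one dose post Day 169". Section 8.7.1.3 then says: "All analyses will be based on as-observed data; hence no imputation will be implemented"; the synopsis has the same rule. For Major and Partial Clinical Response, SAP 8.1.3 adds: "If a subject has any missing data at a particular visit, the subject will be excluded from the analysis at that particular visit". It refers to a separate LTE SAP for details.

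**Who is discontinued.** The LTE steroid rule is worded in three ways:
- Section 3.3.4: "Subjects requiring more than 14 days of rescue therapy will be discontinued", with no dose threshold in that sentence.
- Section 4.5.4.2: "Subjects requiring more than 20 mg/day for more than 14 days of rescue therapy will be discontinued from the LTE".
- Section 3.5: a total daily dose above 20 mg and/or a duration above 14 days.

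Section 3.5 also requires discontinuation when new lupus manifestations need medication that the protocol does not allow.

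**What is observed afterwards.** Section 3.5 sends these subjects to the End of Treatment and Follow-up Day 42 visits. Table 5.1-3 schedules BILAG, SLEDAI-2K and MDGA at both and has no later efficacy visit for them. Section 3.6 asks for continued outcome follow-up, but in line with Section 5, which schedules nothing further.

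**Short-term contrast.** Before Day 169, discontinuation counts as non-response (protocol 8.1; SAP 7.5.1, 8.1.1 and 8.3).

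**The concern.** Durability asks what share of the subjects who entered the LTE are still responding at a later time. The as-observed rate answers a narrower question: what share are responding among those still attending. The two differ when leaving is related to failing, and here part of the leaving is triggered by failing.

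For these subjects the status at later visits is hardly unknown. BICLA counts a steroid increase beyond the protocol allowance, or an added immunosuppressant, as non-response (protocol 1.3.1). A subject discontinued on those grounds is a known failure on the endpoint's own terms, yet drops out of every later denominator.

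The LTE has no placebo arm (protocol 3.1), so no concurrent control would reveal the effect. The planned 90% confidence intervals describe sampling error only. What is at stake is the description of durability, not a test.

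**Working it through.** The documents state no LTE response rate, withdrawal rate or sample size, so there is no LTE figure to reproduce. The stated short-term power has no bearing on this point.

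**Identity.** At a given LTE visit let E be the entrants who could have reached it, L those who have left, w = L/E, and r the responders among those still observed.
- As-observed rate = r / (E − L)
- All-entrants rate, leavers counted as non-responders = r / E
- Ratio = E / (E − L) = 1 / (1 − w), which is at least 1

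The as-observed rate is therefore never the lower of the two. The gap in points is (r/E) × w/(1 − w).

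**Size.** Assumptions: 100 entrants; 50 responders at entry (the 50% is borrowed from the active-arm rate in protocol 8.1); w of 10%, 20% or 30%; those who stay keep their status.

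| Left | Leavers who are non-responders | As-observed | All-entrants | Gap (points) |
|---|---|---|---|---|
| 10 | all | 50/90 = 55.6% | 50/100 = 50.0% | 5.6 |
| 20 | all | 50/80 = 62.5% | 50/100 = 50.0% | 12.5 |
| 30 | all | 50/70 = 71.4% | 50/100 = 50.0% | 21.4 |
| 10 | 80% | 48/90 = 53.3% | 48/100 = 48.0% | 5.3 |
| 20 | 80% | 46/80 = 57.5% | 46/100 = 46.0% | 11.5 |
| 30 | 80% | 44/70 = 62.9% | 44/100 = 44.0% | 18.9 |

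**Direction over time.** Start from 50 responders in 100.
- Ten responders relapse and leave, and ten non-responders also leave: as-observed 40/80 = 50.0%, apparently full maintenance; all-entrants 40/100 = 40.0%.
- Ten responders relapse and leave, and nobody else does: as-observed 40/90 = 44.4%; all-entrants 40.0%. The as-observed rate falls, but by less.

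**Ranking of arms.** Arm A has 35 responders in 70 and no leavers: 35/70 = 50% on either measure. Arm B also starts with 35 in 70, and 14 responders relapse and leave: as-observed 21/56 = 37.5%, all-entrants 21/70 = 30%. Arm B has more withdrawal for flare and still looks worse. The as-observed difference between arms is 50 − 37.5 = 12.5 points, against 50 − 30 = 20 points over all entrants.

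**Who leaves.** The three steroid wordings select different subjects. Rescue at or below 20 mg/day lasting more than 14 days leads to discontinuation under 3.3.4 but not under 4.5.4.2. A dose above 20 mg/day for a few days leads to discontinuation under the 'or' reading of 3.5 but under neither of the others. The denominator depends on which wording a site follows.

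**The case against.** **The LTE is descriptive, without testing or a placebo arm (8.7.1, 8.7.1.3).** True, and it limits the stakes. It does not change what the reported percentage means.

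**The governing LTE SAP is not among the supplied documents.** It may already contain an all-entrants table, numbers per visit or reasons for leaving. SAP 8.1.3 also says that a subject who does not meet the criteria is a non-responder, so a flare seen before exit might be counted. This stands as a limit on certainty. However, 8.7.1.3 itself rules out imputation for all LTE efficacy analyses, and a later plan would have to depart from it.

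**Only some failures are removed, and they may be seen once before they go.** Correct. Day 169 non-responders who completed treatment may enter the LTE and are counted for as long as they stay. A failing subject can be recorded at End of Treatment and follow-up Day 42. A reader might infer that the LTE cannot address durability at all. The documents do not support that: the estimate is informative, but conditional on remaining.

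**Stronger readings that a reader might draw.**
- *LTE rates must rise or hold.* They need not; the 44.4% case is a fall.
- *Arms with more flare withdrawal look better.* Not in general; see arms A and B. Section 8.7.1.3 plans within-group estimates only.
- *The Day 169 and LTE rates sit on one curve with two scales.* No document describes such a curve. LTE entrants must have completed 24 weeks on study medication (3.3.4), so none is a discontinuation-imputed non-responder at Day 169. Setting LTE rates beside the full short-term rate would mainly compare different populations.

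**Counting every exit as failure is biased too.** Also correct. The LTE has no defined end date. Subjects can leave because the sponsor stops the study, an arm is closed (3.1), or a country amendment limits the LTE to one year (SAP Table 2.4-1). Calling those exits loss of response would understate durability, and the fix has to allow for this.

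**Conclusion.** The point holds in a limited form. Protocol 8.7.1.3 fixes an as-observed analysis for a period whose efficacy assessments are meant to show durability, while some failing subjects are discontinued by rule and not assessed after follow-up Day 42. The resulting rates are conditional on remaining in the LTE and are never below the all-entrants rate with leavers counted as non-responders. That inequality is arithmetic and needs no assumption.

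The size cannot be derived from the documents. With 50% response at entry and 10% to 30% withdrawal, all assumed, the gap is 5.6 to 21.4 points if every leaver is a non-responder, which is the extreme case. It is 5.3 to 18.9 points if 80% are. Neither the trend over visits nor the ranking of arms is determined. The Day 169 primary comparison is untouched.

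**What to change.** In protocol 8.7.1.3 and the LTE SAP:

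1. Add a summary of LTE BICLA, SRI(X) and Major and Partial Clinical Response over all subjects with at least one LTE dose who could have reached the visit by the data cut.
2. Count discontinuation for lack of efficacy, flare, rescue or prohibited medication, adverse event, subject withdrawal or loss to follow-up as non-response from that point on.
3. Treat administrative exits (sponsor termination, arm closure, country-specific limit on LTE duration, data cut) as not evaluable, not as failures. Assign any remaining reason in section 3.5, such as pregnancy, to one class in advance.
4. Present this beside the as-observed table, with the number observed and the reasons for leaving at each visit and arm.
5. Reconcile the LTE steroid discontinuation wording in 3.3.4, 3.5 and 4.5.4.2, since it decides who leaves the denominator. Which wording is right is a clinical decision and is not addressed here.

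Cost: a wording change and one extra set of tables, with no new visits or data. The all-entrants LTE rates will look less favourable than the as-observed ones.
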